8.1.1 Discontinuation of Study Intervention

8.1.1. Tier 1 Stopping Rule:

The primary objective of Tier 1 is to assess the feasibility of protocol therapy in subjects with advanced MPNs as measured by the incidence of dose limiting toxicity (DLT, see *Definition of Dose Limiting Toxicity* section). Toxicities are assessed by CTCAEv5 criteria. Up to a total of 12 patients will be accrued to Tier 1. Tier 1 will be stopped for safety considerations under the following conditions:

- Any patient has grade 5 (lethal) DLT occurring within the first 12 weeks of starting vactosertib; or
- More than two patients experience a dose-limiting toxicity (DLT) at any dose, within the first 12 weeks on study.

Trial accrual will be suspended and a DSMB convened if either of these *Tier 1 Stopping Rule* criterion is triggered. If more than two patients have a DLT at the same dose level, then further accrual to that dose level and higher dose levels will be suspended. Pending review with DSMB, the study may be re-opened with amendment reflecting changes to the permitted dose levels. A planned stop to Tier 1 accrual will occur after 12 subjects have received at least one dose of vactosertib. At this time, the DSMB will be convened if fewer than 1 of the first 12 patients experience clinical benefit.

Protocol therapy will be considered safe if the *Tier 1 Stopping Rule* is not triggered. The following table provides the marginal probability of declaring the intervention unsafe for different rates of severe toxicity (as defined by *Tier 2 Stopping Rule*). This *Tier 1 Stopping Rule* protects against an unexpectedly high rate of severe toxicity.

Tier 1	True Rate of Severe Toxicity				
	5%	10%	15%	20%	30%
Probability of Declaring Unsafe	12%	35%	56%	73%	91%

If the Tier 1 safety boundaries are not crossed, this treatment strategy will be considered safe for expansion to Tier 2. Feasibility and toxicity will continue to be monitored in the Tier 2 portion of the study. A total of 37 patients will be accrued (Tier 1 + Tier 2) and the Tier 2 rule stopping rule applies to all subjects (up to 37) enrolled.

8.1.2. Tier 2 Stopping Rule:

- Any patient has grade 5 (lethal) DLT occurring within the first 12 weeks of starting vactosertib; or

- More than five patients experience a dose-limiting toxicity (DLT) at any dose, within the first 12 weeks on study.

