Protocol therapy will be considered safe if the *Tier 2 Stopping Rule* is not triggered. The following table provides the marginal probability of declaring the intervention unsafe for different rates of severe toxicity (as defined by *Tier 2 Stopping Rule*). The *Tier 2 Stopping Rule* protects against an unexpectedly high rate of severe toxicity.

Tier 2	True Rate of Severe Toxicity				
	5%	10%	15%	20%	30%
Probability of Declaring Unsafe	3.1%	31%	67%	89%	99%

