12.5 Interim Analysis

Reports of toxicity and efficacy will be submitted for DSMB review at the following time points:

- completion of Tier1;
- completion of Tier2;
- any time one of the stopping rules is met.

Unscheduled Interim Analysis will be performed if more than three patients have a DLT at the same dose level or if more than five patients in both tiers, at any dose level, have a DLT. In the former situation, further accrual to that dose level and higher dose levels will be suspended. In the latter situation, further accrual to the study will be halted. Reports of toxicity and efficacy will be submitted for DSMB review in that instance for review and guidance as to whether the dose level can be re-opened or accrual to the study can proceed and if the study should be amended to permanently close the problematic dose levels or closed altogether.

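### The safety tables in 8.1.1 and 8.1.2 describe stopping triggers one DLT stricter than the written rules, and the same-dose-level trigger differs between 8.1.1 and 12.5

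*Combined protocol and SAP*

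**What the plan says.** **Tier 1 (section 8.1.1, 12 patients).** Accrual is suspended and the DSMB convened on any grade 5 DLT in the first 12 weeks, or when "More than two patients experience a dose-limiting toxicity (DLT) at any dose, within the first 12 weeks on study". The section adds a dose-level rule: "If more than two patients have a DLT at the same dose level", accrual to that level and those above it is suspended.

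**Tier 2 (section 8.1.2).** The triggers are any grade 5 DLT, or "More than five patients experience a dose-limiting toxicity (DLT) at any dose, within the first 12 weeks on study". Section 8.1.1 makes the count cumulative, since the Tier 2 "stopping rule applies to all subjects (up to 37) enrolled".

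Each rule is followed by a table said to give the "marginal probability of declaring the intervention unsafe for different rates of severe toxicity":

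| True rate | 5% | 10% | 15% | 20% | 30% |
|---|---|---|---|---|---|
| Tier 1, printed | 12% | 35% | 56% | 73% | 91% |
| Tier 2, printed | 3.1% | 31% | 67% | 89% | 99% |

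**Section 12.5** repeats the Tier 2 trial-wide number ("if more than five patients in both tiers, at any dose level, have a DLT") but gives a different dose-level number: "Unscheduled Interim Analysis will be performed if more than three patients have a DLT at the same dose level". The consequence is the same as in 8.1.1: accrual to that level and higher levels is suspended.

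**The concern.** The tables are the plan's only evidence of how well the stopping rules protect patients, and a DSMB or IRB will judge the rules by them. A reader of the Tier 1 table would conclude that a drug with a 20% DLT rate has a 27% chance (100 − 73) of passing into Tier 2. If the text governs, the chance is 56%. At a 30% rate the figures are 9% and 25%.

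The dose-level conflict is a matter of conduct. When a third DLT occurs at one dose level in Tier 2, 8.1.1 calls for suspension of that level and 12.5 does not. No text says which applies.

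**Working it through.** **Inputs.** Tier 1: n = 12, trigger 3 (8.1.1). Tier 2: n = 37 cumulative, trigger 6 (8.1.1, 8.1.2, 12.5). Rates and printed values come from the two tables.

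**Step 1: the printed tables.** The chance of reaching a trigger r among n patients is P(X ≥ r) = 1 − Σ(k < r) C(n,k) p^k (1−p)^(n−k).

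Worked cell, Tier 1 at p = 0.20: P(0) = 0.0687, P(1) = 0.2062, P(2) = 0.2835.
- Trigger 3, as written: 1 − 0.5583 = 44.2%.
- Trigger 2: 1 − 0.2749 = 72.5%. The plan prints 73%.

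All cells, in %:

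| True rate | 5% | 10% | 15% | 20% | 30% |
|---|---|---|---|---|---|
| Tier 1 printed | 12 | 35 | 56 | 73 | 91 |
| ≥3 of 12 (text) | 2.0 | 11.1 | 26.4 | 44.2 | 74.7 |
| ≥2 of 12 | 11.8 | 34.1 | 55.7 | 72.5 | 91.5 |
| Tier 2 printed | 3.1 | 31 | 67 | 89 | 99 |
| ≥6 of 37 (text) | 1.0 | 16.0 | 48.7 | 77.8 | 98.3 |
| ≥5 of 37 | 3.6 | 31.0 | 67.0 | 88.8 | 99.5 |

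The lower triggers match all ten printed cells within 1 point. The written triggers match only the Tier 2 cell at 30%.

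**Step 2: other explanations.** None of these reproduces either table to within 2 points in every column:
- Nearby sample sizes (11 to 13; 25; 35 to 38) with other triggers.
- Following the written rule through both tiers, counting a Tier 1 stop as a stop: 2.6/21.2/53.8/80.5/98.5%.
- Adding the grade 5 trigger, with 2 to 40% of DLTs fatal or an extra fatal risk of 0.5 to 2% per patient. For example, a 20% fatal share gives 12.3/26.9/43.0/58.5/82.2% in Tier 1, which fits only the first column.

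**Step 3: the dose-level conflict.** In Tier 1 it has no effect, because a third DLT at any dose already suspends all accrual.

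For Tier 2, assume:
- Tier 1 passed, with at most 2 DLTs.
- All Tier 2 DLTs fall at the starting level, which normally has no Tier 1 DLTs (6.3.6.3).
- DLTs are non-fatal and known at once.
- The trial-wide trigger is six.

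With at most 2 DLTs carried over, the third or fourth DLT at one level is reached no later than the trial-wide sixth. The mean number of Tier 2 patients treated before a pause (25 if none) is then Σ(i = 0 to 24) P(Bin(i, p) ≤ r − 1). At p = 0.20:
- r = 3 (8.1.1): 14.4
- r = 4 (12.5): 18.2

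The cost of the stricter number appears at a tolerable rate. At p = 0.10 the chance of a pause at some point in the trial is 1 − P(Tier 1 passes) × P(Bin(25, 0.10) ≤ r − 1):
- r = 3: 1 − 0.8891 × 0.5371 = 52%
- r = 4: 1 − 0.8891 × 0.7636 = 32%

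**Step 4: an optional earlier boundary.** Suppose six is kept, and 4 of the first 18 or 5 of the first 24 (both tiers) also pauses accrual. With DLTs spread over levels and a constant rate, the mean number of Tier 2 patients treated, given that Tier 1 passed, changes as follows:

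| Rate | Tier 1 passes | Flat six | With boundary | Saved per trial started |
|---|---|---|---|---|
| 20% | 0.558 | 19.84 | 17.13 | 0.558 × 2.71 = 1.5 |
| 25% | 0.391 | 16.93 | 13.52 | 0.391 × 3.41 = 1.3 |
| 30% | 0.253 | 14.35 | 10.55 | 0.253 × 3.80 = 1.0 |

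The added chance of a pause is at most about 2 points at any constant rate from 5 to 30%. Under a third-DLT same-level rule with all Tier 2 DLTs at one level, the saving per trial started is 0.3 to 0.5 patients.

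**The case against.** **Placement may resolve the dose-level conflict.** The stricter number sits under the Tier 1 heading, while 12.5 is study-wide and mentions both tiers, so 12.5 could be taken to govern Tier 2. That reading is plausible but not settled. In Tier 1 the dose-level rule cannot trigger a pause any earlier than the any-dose count, so reading it as Tier 1 only leaves it little to do. Section 6.3.6.4 also carries the Tier 1 scheme for toxicity monitoring into Tier 2.

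**The grade 5 trigger adds protection that the binomials omit.** This is true, and it lowers the patient counts in Steps 3 and 4. It does not rescue the tables, as Step 2 shows.

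**Stronger readings that a reader might infer, and that the documents do not support:**
- *That the flat cap of six is itself a fault, or that Tier 2 is unmonitored.* The cap is loose early (6/13 = 46%, against 3/12 = 25% in Tier 1), equal to 25% at patient 24, and strict late (6/37 = 16%). Section 12.5 schedules DSMB reports only at completion of each tier. But a flat cap is a legitimate choice here. Tier 1 is an early look, its DLTs count toward the six, one fatal DLT stops the trial, and Table 3 holds and reduces individual doses. The investigator reviews safety continuously (section 15), and any rule that fires goes to the DSMB.
- *That the tables reveal the intended rule.* They fit 2 and 5, but 12.5 repeats more than five. Only the sponsor can say which is right.
- *That the three-patient enrolment hold in 7.7.1 should apply in Tier 2.* Its wording ties it to Tier 1.

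**Conclusion.** Two statements are wrong as written. First, both tables belong to triggers one DLT lower than the text. This rests only on the binomial formula and the plan's own numbers. If the text is the intended rule, the plan overstates its protection by 29 points in Tier 1 (73% against 44%) and 11 points in Tier 2 (89% against 78%) at a 20% rate. If the tables are intended, the text would let the trial run one DLT too long in each tier.

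Second, the dose-level threshold conflicts between 8.1.1 and 12.5. Its size in Tier 2, 14.4 against 18.2 patients, is a bounding figure: it holds at a constant 20% rate under the assumptions in Step 3, with the grade 5 stop not modelled.

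An earlier boundary is a refinement, not a correction. Its gain is about 1.0 to 1.5 patients per trial started at 20 to 30% when DLTs are spread over levels. It would be smaller with fatal DLTs included: about 0.9 to 1.2 at a 20% rate if 5 to 10% of DLTs were fatal, a share the documents do not give.

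**What to change.** 1. **Settle the trial-wide triggers.** Choose 3 and 6 (text) or 2 and 5 (tables), make 8.1.1, 8.1.2 and 12.5 agree, and recompute both tables for the rule used. State whether the tables include the grade 5 trigger. The Tier 1 table should refer to the Tier 1 rule, and 12.5 should carry the 12-week window. The choice is a real trade-off: at a 10% true rate, Tier 1 stops 11% of the time with trigger 3 and 34% with trigger 2.
2. **State one same-level threshold for Tier 2** in both 8.1.1 and 12.5. The third DLT pauses sooner. The fourth gives fewer pauses at a 10% rate (32% against 52%, with triggers 3 and 6 and all Tier 2 DLTs at one level). The choice is the sponsor's.
3. **Optional, only if six is kept:** add to 8.1.2 a suspension with DSMB review if 4 or more of the first 18 patients, or 5 or more of the first 24, both tiers together, have a DLT within 12 weeks.

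Items 1 and 2 cost two recalculated tables and a few aligned numbers, with the existing DSMB and no extra patients. Item 3 adds at most about 2 points to the chance of a pause.

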8.2 Participant Discontinuation/Withdrawal from the Study

Participants are free to withdraw from participation in the study at any time upon request. An investigator may discontinue or withdraw a participant from the study for the following reasons:

- Pregnancy
- Significant study intervention non-compliance
- If any clinical adverse event (AE), laboratory abnormality, or other medical condition or situation occurs such that continued participation in the study would not be in the best interest of the participant
- Disease progression which requires discontinuation of the study intervention
- Participant lost to follow-up after several attempts to contact subject to schedule study visit.

8.3 Lost to Follow Up

A participant will be considered lost to follow-up if he or she fails to return for scheduled visits and is unable to be contacted by the study site staff.

The following actions must be taken if a participant fails to return to the clinic for a required study visit:

- The site will attempt to contact the participant and reschedule the missed visit and counsel the participant on the importance of maintaining the assigned visit schedule and ascertain if the participant wishes to and/or should continue in the study.
- Before a participant is deemed lost to follow-up, the investigator or designee will make every effort to regain contact with the participant (where possible, 3 telephone calls. These contact attempts should be documented in the participant's medical record or study file).
- Should the participant continue to be unreachable, he or she will be considered to have withdrawn from the study with a primary reason of lost to follow-up.

9. Correlative/Special Studies

9.1. On-target Pharmacodynamic Response Reported by SMAD2/3 Phosphorylation

9.1.1. Collection of Specimen(s):

9.1.1.1. Blood specimens are collected at the following times:

9.1.1.1.1. Screening and at End of Tier Testing.

9.1.1.1.2. One hour after observed dose any time a new dose level is used (e.g., following a dose escalation, dose restart, dose reduction).

9.1.1.2. Bone marrow Specimens

9.1.1.2.1. Bone marrow aspirate specimens are collected at Screening and at end of Cycle 4 (16 weeks ± 7 days). In the event of a dry tap, the requirement for the bone marrow aspirate is waived (a biopsy is still required).

9.1.1.2.2. Bone marrow biopsy sections will be obtained at Screening and at end of Cycle 4. Sections will be obtained from hematopathology after clinical evaluation is complete. Unstained, sections will be cut from the residual tissue block. No separate research specimen is required.

9.1.2. Handling of Specimens(s):

9.1.2.1. Blood specimens are collected in standard EDTA (purple top) vacutainer tubes.

9.1.2.2. Bone marrow aspirate specimens will be collected into heparinized syringes and transferred to standard heparin (green top) vacutainer tubes.

9.1.2.3. Bone marrow biopsy sections will be obtained from Weill Cornell Medicine hematopathology director [name], PhD.

9.1.3. Shipping of Specimen(s): Specimens will be hand-delivered to the [name] Lab.

9.2. Molecular Response Reported by JAK2V617F, CALR type 1 or type 2, MPLW515L/K Driver Mutation Variant Allele Frequency

9.2.1. Collection of Specimen(s):

9.2.1.1. Blood specimens are collected at Screening, at end of Cycle 4 (16 weeks ± 7 days) and at End of Tier Test.

9.2.1.2. Bone marrow aspirate specimens are collected at Screening and at end of Cycle 4.

9.2.1.3. Bone marrow biopsy sections will be obtained from hematopathology after clinical evaluation is complete. Unstained, sections will be cut from the residual tissue block. No separate research specimen is required.

9.2.2. Handling of Specimens(s):

9.2.2.1. Blood specimens are collected in standard EDTA (purple top) vacutainer tubes.

9.2.2.2. Bone marrow aspirate specimens will be collected into heparinized syringes and transferred to standard heparin (green top) vacutainer tubes.

9.2.3. Shipping of Specimen(s): Specimens will be hand-delivered to [name] Lab.

10. Measurement of Effect

10.1. Response Criteria (Criteria for Clinical Benefit)

The following criteria are used to decide if subject can be offered the opportunity to receive more than 4 cycles of vactosertib AND for decision to proceed to the Tier 2 expansion phase after Tier 1. These are adapted from the IWG-MRT and ELN consensus reports on response determination in patients with MPNs.

10.1.1 Symptomatic Response

- Defined by a reduction in MPN-SAS total score by $\geq 50\%$ compared to pretreatment score.

10.1.2 Splenic Response

Defined by:

- Non-palpable spleen when baseline spleen size was 5-10 cm below left costal margin;
- At least 50% reduction in spleen size when baseline spleen is > 10 cm below left costal margin
- At least 35% reduction in spleen size as assessed by US, CT or MRI.

Note: A baseline spleen size < 5 cm below left costal margin is not eligible for spleen response;

10.1.3 Erythropoietic Response

Defined by any of the following:

- HGB increase of 1.5g/dL compared to baseline HGB;
- Reduction in PRBC transfusion rate to $\leq 50\%$ of pre-treatment transfusion rate; or
- Reduction in PRBC transfusions by ≥ 4 Units over an 8-week period.

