4.2 Inclusion Criteria

- Age ≥ 18 years
- Patients meet the WHO 2016 criteria for a Ph-neg MPN (including PV, ET, MF, MDS/MPN, MPN-U).
- Patients with MF must have DIPSS+ Intermediate or High-risk MF (primary or post-PV/ET)
- Patients should be on a stable dose of current cytoreductive therapy for at least 3 months prior to C1D1.
- Anemia as defined by HGB < 10 g/dL, or transfusion of ≥ 2 packed red blood cell (PRBC) unit within the past 4 weeks with HGB ≤ 8.5g/dL. The anemia, in the investigator's opinion,

must be due to underlying MPN and not due to other causes such as the toxic effects of prior cytoreductive chemotherapy.

- Ineligible, unsuitable or refractoriness to ESA therapy defined as any of the following:
 - Serum erythropoietin (EPO) >125 U/L⁴.
 - Proven ESA unsuitability is defined by history of any of the following:
 - Loss of erythroid hematologic improvement while receiving stable or increased ESA dose; or
 - ESA-attributed toxicity that, in the treating physician's opinion, makes ESA therapy unsuitable for subject.
 - ESA refractoriness defined by lack of erythroid hematologic improvement to ESA:²⁷
 - Less than 1.5 g/dL increase in hemoglobin after at least 6 weeks of ESA therapy; or
 - Ongoing transfusion dependence that has not been reduced by >4 U over an 8-week period compared to ESA pre-treatment 8 weeks.
- ECOG Performance status ≤ 2
- Able to swallow tablets
- Able to give written informed consent
- Willing and able to comply with scheduled visits, treatment plans, tests and procedures.
- Acceptable Organ Function as defined by:
 - serum creatinine ≤ 2 mg/dL or > 50 mL/min/1.73m² by direct measure
 - AST(SGOT)/ALT(SGPT) ≤ 3 x institutional upper limit of normal
 - Total bilirubin ≤ 2 x institutional upper limit of normal

Note: Subjects with documented diagnosis of Gilbert's Syndrome resulting in elevated total bilirubin levels will be eligible provided all other eligibility criteria are met.

Note: Subjects with total bilirubin 2-3 mg/dL and direct (conjugated) bilirubin in the normal range will be eligible, provided all other eligibility criteria are met.

- Acceptable Cardiovascular status as defined by:
 - Mean QT interval corrected for heart rate using Fridericia's formula (QTcF) ≤ 450 ms for males, and ≤ 470 ms for females on screening ECG.

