g. Baseline HgB is defined as median HgB within 28 days of Cycle 1, Day 1

h. Include erythrocyte transfusion history 8 weeks prior to screening

Tier 2 Schedule of Assessments	Screening	Treatment Tier 2																						End of Tier2 p patients meeting composite response and toxicity endpoints may continue vactosertib		
		Cycle 1			Cycle 2			Cycle 3			Cycle 4			Cycle 5			Cycle 6									
	Pre-study D-28 to -1	Wk1 ^a	Wk2 ^a	Wk3 ^a	Wk4 ^a	Wk5 ^a	Wk6 ^a	Wk7 ^a	Wk8 ^a	Wk9 ^a	Wk10 ^a	Wk11 ^a	Wk12 ^a	Wk13 ^a	Wk14 ^a	Wk15 ^a	Wk16 ^a	Wk17 ^a	Wk18 ^a	Wk19 ^a	Wk20 ^a	Wk21 ^a	Wk22 ^a	Wk23 ^a	Wk24	
Informed Consent Form	X																									
Inclusion/Exclusion Criteria	X																									
Enrollment	X																									
Demographics	X																									
Diagnosis	X																									
Medical History ^b	X	X	X	X	X	X	X	X	X	X	X	X	X	X	X	X	X	X	X	X	X	X	X	X	X	
Vital Signs	X	X	X	X	X	X	X	X	X	X	X	X	X	X	X	X	X	X	X	X	X	X	X	X	X	
Physical Examination ^c	X	X	X	X	X	X	X	X	X	X	X	X	X	X	X	X	X	X	X	X	X	X	X	X	X	
Medications	X	X	X	X	X	X	X	X	X	X	X	X	X	X	X	X	X	X	X	X	X	X	X	X	X	
ECOG	X	X	X	X	X	X	X	X	X	X	X	X	X	X	X	X	X	X	X	X	X	X	X	X	X	
Toxicity / AE assessment	X	X	X	X	X	X	X	X	X	X	X	X	X	X	X	X	X	X	X	X	X	X	X	X	X	
Con Med assessment	X	X	X	X	X	X	X	X	X	X	X	X	X	X	X	X	X	X	X	X	X	X	X	X	X	
Blood tests ^d	X	X	X	X	X	X	X	X	X	X	X	X	X	X	X	X	X	X	X	X	X	X	X	X	X	
Troponin, BNP, CK-MB	X																									X
EPO level	X					X			X										X						X	
Pregnancy test	X																									
Electrocardiogram (EKG) ^e	X	e	e	e	e	e	e	e	e	e	e	e	e	e	e	e	e	e	e	e	e	e	e	e	e	
Echocardiography with Doppler ^f	X																									X
Bone Marrow Aspirate and Biopsy	X																									X
Ultrasound (left upper quadrant)	X																									X
Research blood	X	X				X			X										X						X	
Research Bone Marrow	X																									X
Treatment Administration Form and Compliance assessment		X	X	X	X	X	X	X	X	X	X	X	X	X	X	X	X	X	X	X	X	X	X	X	X	
MPN-SAF form		X	X	X	X	X	X	X	X	X	X	X	X	X	X	X	X	X	X	X	X	X	X	X	X	

*Patients who have completed Tier 1 would not require repeat assessments if done within 28 days of Tier 2 enrollment

- a. Visits are weekly if there is a dose change (escalated or reduced or held for toxicity). Visits are biweekly if dose is maintained. Visits are extended to every 4 weeks (once per cycle) as long as dose is maintained for 4 weeks.
- b. Must record baseline comorbidities, pre-existing symptoms
- c. Spleen size should be recorded

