6.2.2.2. EKG

6.2.2.3. Transthoracic Echocardiogram

6.2.2.4. Abdominal Sonogram of upper left quadrant to record Spleen size

6.2.2.5. History and Physical Exam

6.2.2.6. Record palpated spleen size

6.2.2.7. Record ECOG performance status

6.2.2.8. Bone marrow aspirate (BMA) and biops

6.2.2.9. Collection of Research blood (20mL) and bone marrow specimens (for pSMAD and VAF quantification).

6.2.2.10. Recording of Transfusion History for the two months (8 weeks) prior to screening.

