7.8 General Concomitant Medication and Supportive Care Guidelines

- 1) Transfusions:
 - a) Packed red blood cell (PRBC) transfusions for HGB <7g/dL, or symptomatic anemia, are permitted.
 - b) Platelet transfusions are permitted for bleeding or platelet counts < 10,000/ μ L.
- 2) Growth Factors and Antimicrobials:
 - a) Administration of ESAs is not be permitted on the trial1.
 - b) Administration of GCSF and use of prophylactic antimicrobials for severe neutropenia is permitted at the discretion of the investigator.

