10.2 Duration of Response

10.2.1. Duration of overall response:

The duration of overall response is measured from the time measurement criteria are met for symptomatic, splenic or erythropoietic response (whichever is first recorded) until the first date that recurrent or progressive disease is objectively documented (taking as reference for progressive disease the smallest measurements recorded since the treatment started)

10.2.2. Duration of stable disease:

Stable disease is measured from the start of the treatment until the criteria for progression are met, taking as reference the smallest measurements recorded since the treatment started.

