12.2.2 Composite response/ Toxicity measure

Responding subjects will have met *Criteria for Clinical Benefit* ([section 9.1](#)) for at least 8 weeks. This will ensure that a stable vactosertib dosing schedule can be achieved. Responding subjects will not experience dose limiting toxicity (see *Definition of Dose Limiting Toxicity*). Only subjects meeting all criteria will be considered responders.

Table 5: Composite Response & Toxicity Endpoint

Adequate Response	Meets Criteria for Clinical Benefit
Stable Response	Meets Criteria for Clinical Benefit to vactosertib for \geq 8 weeks
Tolerable	No Dose Limiting Toxicity Experienced

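### Two of the three erythropoietic response criteria can score transfusion effect or chance as drug response, and the two-stage rule has almost no room for it

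*Combined protocol and SAP*

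**What the plan says.** Section 10.1.3 makes any one of three findings enough:

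- Criterion 1: "HGB increase of 1.5g/dL compared to baseline HGB". It carries no condition on transfusion.
- Criterion 2: "Reduction in PRBC transfusion rate to" 50% or less of the pre-treatment rate. It sets no minimum baseline and no on-study period.
- Criterion 3: at least 4 fewer units over 8 weeks. This names a period, and it implies at least 4 units at baseline.

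Transfused patients can enter: section 4.2 admits those with at least 2 "packed red blood cell (PRBC) unit within the past 4 weeks" and HGB of 8.5 g/dL or less, as an alternative to HGB below 10 g/dL. On study, section 7.8 states "Packed red blood cell (PRBC) transfusions for HGB <7g/dL, or symptomatic anemia, are permitted". Baseline haemoglobin does not set aside post-transfusion values: "Baseline HgB is defined as median HgB within 28 days of Cycle 1, Day 1" (section 6.1, footnote g). Item 6.2.2.10 requires "Recording of Transfusion History for the two months (8 weeks) prior to screening".

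The primary composite (section 12.2.2, Table 5) adds durability, "Meets Criteria for Clinical Benefit to vactosertib for" at least 8 weeks, and no DLT. Section 10.2.1 measures response duration "until the first date that recurrent or progressive disease is objectively documented".

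Table 4 sets the no-effect rate at 5%, without a source. Section 12.4.2 cites rates on best available therapy of at most 10% for clinical improvement and at most 3% for splenic or erythropoietic response. Section 10.1 describes its criteria as adapted from published consensus reports.

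**The concern.** This is a single-arm trial, so its error control rests entirely on the assumed response rate without drug effect. Two routes can produce a response without drug effect. A transfusion can raise haemoglobin by 1.5 g/dL over baseline, and nothing in criterion 1 excludes that rise. Transfusion counts also vary from one period to the next, so a patient who had 1 unit before treatment and none on study meets criterion 2.

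The protocol applies comparable safeguards elsewhere. Table 3 treats any erythrocyte transfusion as an inadequate erythropoietic response, section 10.1.2 excludes small baseline spleens from splenic response, and the ESA-refractoriness criterion in section 4.2 compares one 8-week period with another.

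The same patient can therefore be a responder or not, depending on who scores and over which weeks. In an open-label trial, choosing the reading after the data are in could decide the go/no-go result.

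**Working it through.** **1. The plan's own design.** Inputs from Table 4: 12 patients with at least 1 responder to continue, 37 in total with at least 4 to succeed, no-effect rate 0.05, target rate 0.20.

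P(go) = sum over x from 1 to 12 of P(X1 = x) × P(X2 ≥ max(0, 4 − x)), with X1 ~ Bin(12, p) and X2 ~ Bin(25, p).

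- p = 0.05: 9.35%, so the stated limit of 10% is reproduced.
- p = 0.20: 90.2%, so the stated power is reproduced.
- P(go) = 10% at p = 0.0512.
- p = 0.08: 29.4%.

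The arithmetic is right. The margin is about 0.1 percentage point of no-effect rate (5.12% − 5%).

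**2. Does the text elsewhere close the gaps?**

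| Gap | Table 5 (12.2.2) | Section 10.2.1 |
|---|---|---|
| HGB rise in a transfused patient | Not barred | Not addressed |
| Halving from a very low baseline | Not barred | Not addressed |
| On-study period for a rate | At least 8 weeks of benefit, but not how a rate is met over them | Ends response only at recurrence or progression |

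**3. How large could the chance effect be?** The documents give neither the share of patients transfused nor their need. The following are assumptions: 25% of patients are transfused; units in each period are independent Poisson counts with unchanged mean m = 2, 4 or 6 per 8 weeks; nothing else produces a response.

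*One fixed 8-week window, criteria 2 or 3.* With X units before and Y after, the chance response is q = sum over x ≥ 1 of P(X = x) × P(Y ≤ max(⌊x/2⌋, x − 4)). The no-effect rate is p = 0.25 × q.

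| m | q | p | False-go |
|---|---|---|---|
| 2 | 0.320 | 0.080 | 29% |
| 4 | 0.224 | 0.056 | 13% |
| 6 | 0.185 | 0.046 | 7.6% |

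The false-go rate passes 10% when the transfused share exceeds 0.0512/q, which is 16%, 23% and 28%.

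*Adding the no-DLT condition.* With an assumed, independent 10% DLT rate, p becomes 0.9 × 0.25 × q, and the false-go rate is 23%, 9.5% and 5.6%.

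*Whole tier, criterion 2 only.* Over 16 weeks Y has mean 2m and must be at most X. Over 24 weeks it has mean 3m and must be at most 1.5X. This gives q = 0.268, 0.154, 0.095 for the 12 Tier 1 patients and 0.194, 0.104, 0.060 for the 25 Tier 2 patients. The false-go rate is 13%, 2.2% and 0.4%.

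*The bar of more than 7 of 37 in section 12.4.2.* With the fixed window and 25% transfused, P(X ≥ 8) for X ~ Bin(37, p) is 0.8%, 0.09% and 0.02%. At 40% transfused and m = 4 (p = 0.40 × 0.2239 = 0.090) it is 1.5%. At 40% and m = 2 (p = 0.40 × 0.3196 = 0.128) it is 9.2%.

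The effect of transfusion on the haemoglobin criterion was not quantified; the documents give nothing to base it on.

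**The case against.** Much of the case for leaving the plan alone has force.

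- A reader might infer that the definition has no floor and no period at all. It does not read that way: criterion 3 has both, and Table 5 requires at least 8 weeks of benefit in the primary composite. What stands is that neither bars transfusion under criterion 1 nor says how a rate is met for 8 weeks.
- A reader might infer that the no-effect rates belong to some other endpoint. They do not: sections 12.1.1 and 12.4.2 apply them to this same named composite. The accurate statement is that the 5% has no source and that the rates of at most 10% and at most 3% are not shown to use this adapted definition.
- The Tier 1 schedule appears to mark the composite assessment once, at end of tier. That makes it a strained reading that any favourable 8-week stretch counts, and no figure here relies on it. It still does not define a window.
- The size rests on invented inputs. Requiring no DLT lowers it, whole-tier scoring puts it below the design value at means of 4 and 6, and the bar for a randomized study is barely touched at 25% transfused.
- Table 3 is a dosing rule and need not match an endpoint. That is fair, but items 6.3.2.1.8 and 6.3.5.10 point to it for the erythropoietic response assessment, so the documents should say which one defines the endpoint.

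**Conclusion.** The point holds as a gap in the endpoint definition. As written, a transfusion-driven haemoglobin rise, or a chance fall from a low transfusion baseline, can score as a response in a decision rule that tolerates a no-effect rate of only about 5.1%.

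It is tempting to conclude that the type I error exceeds 10%. The documents do not support that. It depends on the transfused share, the transfusion need, the DLT rate and the on-study period, none of which they give. Under the stated assumptions the false-go rate runs from 0.4% to 29%, against 9.35% by design. It is clearly above design at a mean of 2 units with a fixed window, near design at 4, and below it at 6. Inflation is possible, not demonstrated. The plan should settle the definition before patients are scored. Confidence is medium.

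**What to change.** 1. In 10.1.3, score the haemoglobin criterion only when the rise is met with no red cell transfusion during the response period of at least 8 weeks. This is a scoring condition and places no limit on transfusion.
2. Prespecify one on-study 8-week period, the same in both tiers, compared with the recorded 8-week history, for both transfusion criteria.
3. State that 10.1.3 defines the endpoint, reconcile the references to Table 3 in 6.3.2.1.8 and 6.3.5.10, and change the pointers to section 9.1 in the protocol summary and in 12.2.2 to 10.1 (9.1 is the SMAD2/3 section).
4. State in 12.1 that type I error is below 10% only if the no-effect rate of this composite is at most about 5.1%, and give the basis for the 5%.

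The cost is an amendment to a primary-endpoint definition. No new data are needed, because haemoglobin, transfusions and the 8-week history are already recorded. Somewhat fewer patients will count as responders, and power of 90.2% has little slack; the power cost of items 1 and 2 was not computed and should be checked.

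A minimum baseline unit count for criterion 2 is optional and for the sponsor to decide, because it trades power for error control. In the fixed-window illustration a 2-unit floor moves the false-go rate from 29%, 13%, 7.6% to 22%, 12%, 7.6%, and a 4-unit floor to 1%, 8%, 7.3%. If a quarter to a half of true responders qualify only through transfusion, with an assumed 75% true fall in need, the 4-unit floor leaves power between 58% and 89%.
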